**16.25 Operating Characteristics**

The probability of declaring that this regimen warrants further studies (i.e. statistical power) under various success proportions and the probability of

stopping accrual after the first stage can be tabulated as a function of the true success proportion as shown in the following table.

If the true success proportion is:	0.05	0.1	0.15	0.2
then the probability of declaring that the regimen warrants further studies is:	0.08	0.35	0.63	0.82
and the probability of stopping at stage 1 is:	0.54	0.28	0.14	0.07

### 16.25 Other Considerations

Adverse events, quality/duration of response, and patterns of treatment failure observed in this study, as well as scientific discoveries or changes in standard of care will be taken into account in any decision to terminate the study.

## 16.3 Analysis Plan

The analysis for this trial will begin at planned time points (see 16.2) and at the time the patients have become evaluable for the primary endpoint. Such a decision will be made by the Statistician and Study Chair, in accord with CCS Standard Operating Procedures, availability of data for secondary endpoints (e.g. laboratory correlates), and the level of data maturity.

### 16.31 Primary Objective

#### 16.311 Definition

The primary endpoint for this study is overall response rate (ORR) at 36 weeks after registration, which is defined as the percentage of patients, among evaluable patients, who experience an objective response.

Objective response is defined as a complete or partial response per RECIST v1.1, without the confirmation scan. The evaluable patients are those who are eligible, consented, received any protocol treatment, and are not major violations.

#### 16.312 Estimation

The proportion of successes will be estimated by the number of successes divided by the total number of evaluable patients. Confidence intervals for the true success proportion will be calculated according to the approach of Clopper and Pearson.

#### 16.313 Over Accrual

If more than the target number of patients are accrued, the additional patients will not be used to evaluate the stopping rule or used in any decision making process. However, they will be included in final point estimates and confidence intervals as though they were accrued in the final stage.

## 16.32 Secondary Objectives

The following objectives will be evaluated: clinical benefit rate, progression-free survival, overall survival, and adverse event rates. Historical controls will be used for comparisons when appropriate.

#### 16.321 Clinical Benefit Rate

Clinical Benefit Rate is defined as the number of patients that experience a complete or partial response within 36 weeks post registration, or have stable disease for at least 36 weeks post registration, divided by the number of evaluable patients. Analysis of this endpoint will mirror that of the primary objective (section 16.31).

#### 16.322 Progression-free Survival

Progression-free survival (PFS) is defined as the time from study entry to the first of either disease progression or death from any cause, where disease progression is determined based on RECIST 1.1 criteria. PFS will be estimated using the Kaplan-Meier method. The median PFS and corresponding 95% confidence interval will be reported. Patients who do not experience disease progression or death while on protocol will be censored at the last disease assessment date.

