## 13.0 Treatment/Follow-up Decision at Evaluation of Patient

- 13.1 Patients who have CR, PR, or SD will continue treatment per protocol up to 35 cycles. After 35 cycles, patients will go to event monitoring.
- 13.2 Patients who develop PD while receiving therapy will go to the event-monitoring phase.
- 13.3 Patients who go off protocol treatment for reasons other than PD or alternative therapy will go to the event-monitoring phase per Section 18.0.
- 13.4 Event monitoring is every 3 months for 3 years after registration. If patient is still alive 3 years after registration, no further follow up is required.
- 13.5 A patient is deemed *ineligible* if after registration, it is determined that at the time of registration, the patient did not satisfy each and every eligibility criteria for study entry. The patient may continue treatment off-protocol at the discretion of the physician as long as there are no safety concerns, and the patient was properly registered. The patient will go directly to the event-monitoring phase of the study (or off study, if applicable).
  - If the patient received treatment, all data up until the point of confirmation of ineligibility must be submitted. Event monitoring will be required per Section 18.0 of the protocol.

- If the patient never received treatment, On-study material and the Off Treatment Form must be submitted. No further data submission is necessary.

13.6 A patient is deemed a *major violation*, if protocol requirements regarding treatment in cycle 1 of the initial therapy are severely violated that evaluability for primary end point is questionable. All data up until the point of confirmation of a major violation must be submitted. The patient will go directly to the event-monitoring phase of the study. The patient may continue treatment off-protocol at the discretion of the physician as long as there are no safety concerns, and the patient was properly registered. Event monitoring will be required per Section 18.0 of the protocol.

13.7 A patient is deemed a *cancel* if he/she is removed from the study for any reason before any study treatment is given. On-study material and the Off Treatment Form must be submitted. No further data submission is necessary.

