#### Follow-up Material(s)

CRF	Event Monitoring Phase 				
	q. 3 months until PD	At PD	After PD q. 3 mos.	Death	New Primary
Patient Status: Survival and Disease Status Follow-Up/Event Monitoring	X 	X 	X	X	At each occurrence
Adverse Events: Late 					X
Supporting Documentation 					
Notice of New Primary 					X
Consent Withdrawal (choose appropriate form) 					X
• Consent Withdrawal: Specimen Only					

CRF	Event Monitoring Phase 				
	q. 3 months until PD	At PD	After PD q. 3 mos.	Death	New Primary
• Consent Withdrawal: All Follow-Up					
Lost to Follow-Up 					

1. If a patient is still alive 3 years after registration, no further follow-up is required.
2. Upload a copy of documentation of response or progression in RAVE on the Supporting Documentation Form.
3. Submit only if applicable.
4. Patients are eligible to be confirmed lost to follow-up after 2 years of unsuccessful contact with the patient.

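### The PFS censoring rule turns on the undefined term *on protocol*, which can be read to censor progression and death recorded in event monitoring, and OS inherits the rule

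*Combined protocol and SAP*

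**What the plan says.** Section 16.322 defines PFS as "the time from study entry to the first of either disease progression or death from any cause", with progression judged by RECIST 1.1. It sets no limit to the treatment period. It continues: "PFS will be estimated using the Kaplan-Meier method", with the median and a 95% confidence interval. The paragraph ends: "Patients who do not experience disease progression or death while on protocol will be censored at the last disease assessment date". Section 16.323 says that the OS analysis follows that of PFS.

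Follow-up continues after treatment. Section 13.3 states: "Patients who go off protocol treatment for reasons other than PD or alternative therapy will go to the event-monitoring phase per Section 18.0". Section 13.2 sends patients who progress on therapy to the same phase, and 13.1 sends those who complete 35 cycles. Section 13.4 states: "Event monitoring is every 3 months for 3 years after registration". The follow-up table in Section 18.1 requires a survival and disease status form under the column "q. 3 months until PD", and again at progression, after progression and at death. Its footnote reads: "Upload a copy of documentation of response or progression in RAVE on the Supporting Documentation Form".

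**The concern.** The definition and the censoring sentence can give different answers for the same patient. Someone who stops for toxicity without progression and dies three months later has an event under the definition. Under the last sentence that patient may be censored at the last scan, depending on what *on protocol* means. Two analysts could draw different PFS curves from the same data, which a pre-specified rule should prevent.

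If such patients are censored, Kaplan-Meier assumes that their later risk equals that of patients who stay on treatment. Where it differs, the estimate is biased. Section 16.32 also foresees comparison with historical controls where appropriate, and a median that depends on an undefined term is a weak basis for that. The OS cross-reference raises the stakes, because most OS events would be expected after treatment has ended.

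**Working it through.** **1. The two readings.**

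- *Narrow (on protocol = on protocol treatment).* Section 13.3 speaks of leaving protocol treatment. Sections 13.5 and 13.6 say of patients who move to event monitoring: "The patient may continue treatment off-protocol at the discretion of the physician as long as there are no safety concerns".
- *Broad (on protocol = in the study).* Section 13.5 calls event monitoring a phase of the study, distinguishes it from being off study, and requires it under Section 18.0.

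Neither reading is ruled out. Only the broad one agrees with the PFS definition.

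**2. Who is affected.** Patients can leave without progression through permanent discontinuation for toxicity (8.2), a dosing delay of more than 42 days (8.3), or completion of 35 cycles (13.1). The only rate in the documents is from the earlier study in Section 1.4: 11/106 = 10.4% stopped pemigatinib monotherapy for adverse events. Applied to the maximum accrual of 24 (16.22), this gives 24 × 11/106 = 2.5 patients.

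**3. Size for PFS.** The plan states no PFS figure, so there is none to reproduce. The following is an illustration on assumptions.

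- On-treatment PFS is exponential with an assumed median of 4 months: λ = ln 2 / 4 = 0.1733 per month.
- A share f leaves before progression or death, at constant rate c = λf/(1 − f). For f = 0.104, c = 0.0201.
- After leaving, the hazard is kλ. The multiplier k is assumed.
- Events are observed continuously, with no scan grid.

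Under the narrow rule, Kaplan-Meier estimates exp(−λt), so the median is 4.00 whatever k is. With every event counted,

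S(t) = exp(−(λ+c)t) + [c/(λ+c−kλ)] × [exp(−kλt) − exp(−(λ+c)t)].

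Check for f = 0.104, k = 2, t = 3.88: 0.4722 + [0.0201/(0.1934 − 0.3466)] × (0.2606 − 0.4722) = 0.4722 + 0.0278 = 0.500. The true median is therefore 3.88, and the narrow rule overstates it by 4.00/3.88 − 1 = 3%.

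True median in months, with the error of the narrow rule in brackets:

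| Share leaving | k = 0.5 | k = 1 | k = 2 | k = 4 |
|---|---|---|---|---|
| 10.4% | 4.09 (−2%) | 4.00 (0) | 3.88 (+3%) | 3.76 (+6%) |
| 20% | 4.20 (−5%) | 4.00 (0) | 3.76 (+6%) | 3.53 (+13%) |
| 30% | 4.35 (−8%) | 4.00 (0) | 3.62 (+10%) | 3.29 (+22%) |

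A simulation of 400,000 patients per cell agrees to within about one percentage point. A 2-month median gives nearly the same percentages.

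**4. Against sampling error.** With 24 patients, all with events, and the same exponential assumption, an approximate 95% interval for a 4-month median is 4 × exp(±1.96/√24) = 2.7 to 6.0 months. At 10.4% leaving, the shift is small beside it.

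**5. OS.** Patients who progress on therapy go to event monitoring (13.2). Under the narrow reading their later deaths would be censored, leaving few OS events beyond deaths on treatment. Under the broad reading deaths count, but mirroring PFS still censors survivors at the last disease assessment. The test schedule (4.1) lists no scans after end of treatment, while survival status is collected for up to 3 years. Time known to be alive would then be discarded for survivors while late deaths count, which tends to understate OS.

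**The case against.** The strongest reply is that the narrow reading is unlikely to be intended. The phrases in Section 13 describe treatment, not follow-up, and those in 13.5 and 13.6 concern ineligible patients and major violations. The PFS definition has no on-treatment limit, and applying the narrow reading to OS would make three years of survival follow-up nearly pointless. This stands as evidence of intent. It leaves the term undefined and does not help an analyst who applies the sentence as written.

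A reader might infer that the plan discards post-treatment events and therefore lengthens PFS. The documents support neither step. Discarding is a risk of the wording, not a stated rule. Lengthening needs a higher hazard after stopping, which is plausible but shown nowhere. With equal hazards there is no bias, and with a lower hazard PFS is shortened.

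Some safeguards also narrow the problem. Section 11.45 has symptomatic deterioration reported as progression, and 4.1 requires an end-of-treatment scan if more than 28 days have passed since the last one. These help only in part, because 16.322 ties progression to RECIST 1.1 and does not say whether symptomatic deterioration counts as a PFS event.

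Finally, PFS is secondary and has no hypothesis test. That is correct and limits the weight of the point.

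**Conclusion.** The point holds as a conflict of wording that should be removed, and it is minor. The censoring sentence can contradict the PFS definition beside it, and one supported reading would censor events that the trial collects. It does not establish that PFS will be overstated. At the only documented stopping rate, 10.4% from an earlier study of mixed malignancies, doses and schedules, the illustrated shift in the median is about -2% to +6% for assumed hazard multipliers of 0.5 to 4. The -8% to +22% at 30% stopping needs a rate that the documents do not give.

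The consequence for OS is the larger one: the narrow reading would drop deaths after progression, and the broad reading still uses an unsuitable censoring date for survivors. The two-stage decision on response by 36 weeks (16.21) does not use PFS or OS and is unaffected.

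**What to change.** In 16.322, delete *while on protocol* and write, for example: *The first progression or death from any cause is an event whether recorded during protocol treatment or in event monitoring. Only patients with neither are censored, at their last disease assessment.* Add whether symptomatic deterioration (11.45) counts as progression, and how new anticancer therapy and long gaps between assessments are handled.

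In 16.323, replace the cross-reference with a separate rule: *All deaths count, whenever recorded. Survivors are censored at the date last known alive.*

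The cost is a few sentences. Status, progression documentation and deaths are already requested in event monitoring. There are two small downsides. Median PFS may be slightly less favourable. Progression dates after treatment will also be less precise, because no scans are scheduled after end of treatment and the RECIST measurement form is listed only for treatment and end of treatment (18.1). The report should state how many PFS events came from event monitoring.

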#### 16.323 Overall survival

Overall survival (OS) is defined as the time from study entry to death from any cause. Analysis of this endpoint will mirror that of PFS (section 16.322).

#### 16.324 Patient-reported Outcomes

Patient reported quality of life (QOL) outcomes will be collected using the Linear Analog Self-Assessment (LASA) Questionnaire. Data will be collected each cycle. Mean values of the first question (regarding overall QOL) at each cycle will be plotted. Additional analyses using data collected from the LASA questionnaire may be performed but will be considered exploratory.

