#### 2.2 Secondary

2.21 To assess the clinical benefit rate (complete response + partial response + stable disease ) with Pemigatinib .

2.22 To assess progression free survival (PFS) and overall survival (OS) with Pemigatinib.

2.23 Assess changes in patient quality of life (QOL) as measured by the linear analogue self-assessment (LASA) questionnaire.

2.24 Assess the frequency and severity of adverse events.

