10. Administrative Scheduling Window: After Cycle 1, Day 1, allowance of  $\pm 3$  days for subsequent study visits is permitted for scheduling considerations other than adverse event management (e.g. holidays, weekends, inclement weather).
11. End-of -Treatment (EOT): Reasonable effort should be made to complete End-of-Treatment (EOT) procedures on the day it is decided a patient will no longer receive Pemigatinib. These procedures must be completed subsequent to and not later than 14 days after investigator decision to permanently discontinue Pemigatinib and prior to any subsequent anti-cancer therapy. CT/MRI required at EOT only if it has been  $>28$  days since the previous CT/MRI.
12. Safety Follow-Up: One-month follow-up (1M F/U) visit to be performed 30 to 35 days after the EOT visit. (In the event EOT visit not performed, then the safety follow-up visit is to be performed 30-35 days after the last dose of Pemigatinib.) Any adverse event in the Safety Follow-up will be recorded on the adverse event assessment form in the last cycle of treatment. The Safety Follow-up is recommended by the study protocol, but no data collection is required other than adverse event assessment.
13. Patients have the option to complete cfDNA testing at study completion and will be allowed to re-register with protocol ACCRU-GI-1611. Site will access results by creating an account at [REDACTED]. Sites will be notified by Guardant Health via email when results are available in the portal. See section 13.8. See detailed instructions on the ACCRU website under Manuals and Forms. Kits are required for this collection.
14. If screening tests occur  $\leq 3$  days prior to C1 D1, they do not have to be repeated prior to dosing.
15. Coagulation Panel: to be done at screening, restaging (day 1 of cycles 4, 7, 10 etc.) and end of treatment.
16. Urinalysis: to be done at screening and restaging (day 1 of cycles 4, 7, 10, etc.).
17. Mandatory blood sample-Whole blood: May occur prior to treatment on cycle 1 day 1. Refer to section 14.0
18. Tumor Blood Biomarkers (CEA): to be done  $\leq 7$  days prior to registration, and day 1 of every cycle thereafter.

19. Patient questionnaire will be completed at baseline, day 1 of each cycle, and end of treatment (within 30 days of last dose as noted in appendix V). Patient questionnaire booklets must be used; copies are not acceptable for this submission. The booklet order form is located on the ACCRU website under Manuals and Forms.

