## 11.44 Overall Objective Status

The overall objective status for an evaluation is determined by combining the patient's status on target lesions, target lymph nodes, non-target lesions, non-target lymph nodes, and new disease as defined in the following tables:

For Patients with Measurable Disease

Target Lesions & Target Lymph Nodes	Non-Target Lesions & Non-Target Lymph Nodes	New Sites of Disease	Overall Objective Status
CR	CR	No	CR
CR	Non-CR/Non-PD	No	PR
PR	CR Non-CR/Non-PD	No	PR
CR/PR	Not All Evaluated*	No	PR**
SD	CR Non-CR/Non-PD Not All Evaluated*	No	SD
Not all Evaluated	CR Non-CR/Non-PD Not All Evaluated*	No	Not Evaluated (NE)
PD	Unequivocal PD CR Non-CR/Non-PD Not All Evaluated*	Yes or No	PD
CR/PR/SD/PD/Not all Evaluated	Unequivocal PD	Yes or No	PD
CR/PR/SD/PD/Not all Evaluated	CR Non-CR/Non-PD Not All Evaluated*	Yes	PD

\*See Section 11.431

\*\* NOTE: This study uses the protocol RECIST v1.1 template dated 2/16/2011. For data collection and analysis purposes the objective status changed from SD to PR in the ACCRU protocol RECIST v1.1 template as of 2/16/2011 and to match RECIST v1.1 requirements.

11.45 Symptomatic Deterioration: Patients with global deterioration of health status requiring discontinuation of treatment without objective evidence of disease progression at that time, and not either related to study treatment or other medical conditions, should be reported as PD due to "symptomatic deterioration." Every effort should be made to document the objective progression even after discontinuation of treatment due to symptomatic deterioration. A patient is classified as having PD due to "symptomatic deterioration" if any of the following occur that are not either related to study treatment or other medical conditions:

- Significant worsening of tumor-related symptoms as per investigator discretion.
- Decline in performance status to  $\geq 3$  on ECOG scale.

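### The QOL goal is change, but section 16.324 commits only to a plot of raw item-1 means by cycle, with no change from baseline and no role for the end-of-treatment score

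*Combined protocol and SAP*

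**What the plan says.** Section 2.2 lists as secondary goal 2.23: "Assess changes in patient quality of life (QOL) as measured by the linear analogue self-assessment (LASA) questionnaire".

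Note 19 to the test schedule (section 4.1) sets the collection times: "Patient questionnaire will be completed at baseline, day 1 of each cycle, and end of treatment". The schedule table places the first form at Cycle 1 Day 1.

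Section 16.324 repeats only that data are collected each cycle, and then commits to one output: "Mean values of the first question (regarding overall QOL) at each cycle will be plotted". Anything further is left open: "Additional analyses using data collected from the LASA questionnaire may be performed but will be considered exploratory". Section 16.32, which lists the secondary objectives to be evaluated, does not mention QOL.

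Two routes off treatment bear on who completes the form. Section 13.2 states: "Patients who develop PD while receiving therapy will go to the event-monitoring phase". Section 11.45 classes as progression "Patients with global deterioration of health status requiring discontinuation of treatment without objective evidence of disease progression at that time", with worsening tumor-related symptoms or a decline in ECOG status to 3 or more as its criteria. The event-monitoring forms in section 18.1 consist of "Patient Status: Survival and Disease Status Follow-Up/Event Monitoring" together with event-driven forms. None of them is a LASA.

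**The concern.** A goal about change needs a measure of change. The difference between two plotted means has two parts: how the patients still on treatment have changed, and how they differed at the start from those who have left. The plot cannot separate these. Patients who leave because their disease or general health has worsened are likely to report lower QOL, so the second part probably pushes the later means upward.

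A report that follows section 16.324 exactly could show stable or improving QOL while individual patients decline. The scores that would show this are already mandatory: a baseline score for each patient, and an end-of-treatment score that is the only scheduled form designed to catch patients as they leave. What is at stake is the reading of one descriptive secondary goal.

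**Working it through.** The documents state no QOL effect size, SD or power, so there is no plan figure to reproduce. The check has three steps.

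**1. Goal against analysis**

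| Element needed for goal 2.23 | Collected? | Used in 16.324? |
|---|---|---|
| Baseline item 1 (Cycle 1 Day 1) | Yes | Only as a point in the plot |
| Item 1 on day 1 of each later cycle | Yes | As a raw mean |
| Item 1 at end of treatment | Yes | No role given |
| Within-patient change, with an interval | Can be derived | Not planned |
| Number contributing at each cycle | Can be derived | Not required |

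**2. Hand arithmetic on assumed scores**

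Take the 21 evaluable patients of section 16.22. Suppose 10 start at 5 and 11 start at 8. The baseline mean is (10×5 + 11×8)/21 = 138/21 = 6.57. Let k low scorers leave and let every score move by d. Then

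later raw mean = [(10−k)(5+d) + 11(8+d)] / (21−k),

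and the paired change among those remaining is d.

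| Low scorers leaving (k) | Raw shift, d = 0 | Raw shift, d = −1 |
|---|---|---|
| 0 | 0 | −1.00 |
| 5 | +0.49 | −0.51 |
| 8 | +0.97 | −0.03 |
| 10 | +1.43 | +0.43 |

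For example, with k = 8 and d = −1 the later mean is (2×4 + 11×7)/13 = 85/13 = 6.54. The plot is flat although every patient has lost a point. With a narrower assumed spread (10 at 6, 11 at 7) and d = −1, the raw shift runs from −1.00 to −0.52, so the decline is understated but not hidden.

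**3. Simulation with graded dropout**

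Assumptions: 20,000 trials per scenario, 21 patients each. Item 1 at baseline is N(6.5, SD 2), and reported scores are limited to 0-10, which gives a cycle 1 mean of 6.47. The chance of leaving in a cycle is 1 − exp(−h), with h = (ln 2/median) × exp(−b(QOL − 6.5)/2). Here b is the fall in log-hazard per SD of higher QOL, and the median is time on treatment in cycles. In scenarios 1-3 the hazard uses the baseline score. In scenario 4 it uses the current score, and slopes vary with SD 0.3 per cycle. The mean slope in scenarios 3 and 4 is −0.15 per cycle, or −0.90 over the six cycles to cycle 7. In scenario 3 the 0-10 limit makes this −0.88.

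Cycle 7 minus cycle 1:

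| Scenario | Quantity | b = 0 | 0.1 | 0.25 | 0.5 |
|---|---|---|---|---|---|
| 1. No change, median 3 cycles | Raw means | 0 | +0.24 | +0.61 | +1.07 |
| 2. No change, median 6 cycles | Raw means | 0 | +0.13 | +0.32 | +0.63 |
| 3. True loss 0.88, median 3 | Raw means | −0.87 | −0.61 | −0.25 | +0.23 |

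In scenario 3 the paired change among those remaining is −0.88 to −0.85. In scenario 4 (true mean change −0.90, median 3) the raw-mean difference runs from −0.90 to +0.59 as b rises, and the paired change from −0.90 to −0.55.

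With a median of 3 cycles, about 10 patients contribute at cycle 4 and about 5 at cycle 7. The trial-to-trial SD of the raw difference in scenario 1 is 0.7-0.9. With a median of 6 cycles, about 10 contribute at cycle 7. Limiting the baseline score before the slope is applied, rather than each visit's score, moves scenario 3 only slightly: raw −0.90 to +0.17 against paired −0.90.

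**The case against.** The strongest reply is that the gap is narrow and the endpoint minor. The first form is completed on Cycle 1 Day 1, so the plot does start at baseline and shows the group trend from there. QOL carries no hypothesis or threshold, a change analysis is permitted under the exploratory sentence, and no data are lost. All of this is true and limits the weight of the point. But a trend in means over different sets of patients is not how patients changed, and a permitted analysis is not a planned one.

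The size is also open to challenge. It rests wholly on assumed inputs. It is zero if leaving is unrelated to QOL, it lies well inside trial-to-trial variation when the link is weak, and the sign reverses in scenario 3 only at the strongest link tried. The model uses a constant hazard per cycle, whereas restaging every 9 weeks would cluster exits after cycles 3 and 6. These limits stand: the figures show direction and possible range, and are not a forecast.

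The model also has no measurement error, which could flatter paired change. Adding visit-to-visit error with SD 1 leaves the paired mean essentially unbiased and less variable than the raw difference, so this objection does not change the choice.

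Finally, the remedy is partial. Scenario 4 shows that paired change among those remaining is still selective. End-of-treatment scores are taken at different times, and the sickest patients are the least likely to return that form. This stands and should be stated in the plan.

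**Conclusion.** The concern holds. That section 16.324 plans no measure of within-patient change and gives the end-of-treatment score no role is certain from the text. The practical effect cannot be quantified from the documents. Under the assumptions shown, the raw-mean plot overstates later QOL by between 0 and about 1.1 points of 10 by cycle 7 when nothing has changed, and at the strong end of the range it turns a true loss of 0.88 into an apparent gain of 0.23. Paired change keeps the right sign in every scenario tried, though it is still understated when dropout follows the current score. The impact is confined to one descriptive secondary goal. The ORR decision rule is unaffected. The change is worth making because it measures what goal 2.23 names, with data already being collected.

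**What to change.** Amend section 16.324 as follows:

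- Make the planned summary the within-patient change in LASA item 1 from the Cycle 1 Day 1 score, by cycle and at end of treatment, each with a 95% CI and the number of patients contributing.
- Report the end-of-treatment change alongside time on treatment, because it is taken at different times. It lets patients who leave contribute a last score: all 21 if every form is returned, which is a best case.
- Keep the raw-mean plot as a display, with the number contributing printed at each cycle.
- State that per-cycle change among patients still on treatment remains selective.
- Optionally, add a mixed model using all available scores as a sensitivity analysis.

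The cost is SAP wording and minor programming. No new data, visits or forms are needed.
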